Persistent diarrhoea continues to be an important cause of childhood morbidity and mortality in the developing countries. Improved case management might prevent mortality and morbidity due to this childhood illness. This study proposes to evaluate the feasibility and efficacy of a dietary treatment algorithm (shown efficacious in the hospital setting) as a home based management of children with non-severe persistent diarrhoea. This is a randomised, controlled, home-based intervention study. After examining the eligibility criteria the patients will be randomised to either intervention group (dietary treatment algorithm) or control (standard management). Patients in the intervention group, in addition to dietary manipulation, will receive oral rehydration therapy and vitamin-mineral supplementation. The initial diet (diet A) contains rice powder, cow's milk, and vegetable oil, and calorie content of 68 kcal/100 g. The diet B (containing rice powder, vegetable oil, egg white and sugar and calorie content 68 kcal/100 g) will be offered if there is no improvement of diarrhoea on day 7. Diet B will also be fed for 7 days. The patients under control group will receive standard management which include oral rehydration therapy and his/her usual diet or as advised by hospital physician, and also they will receive vitamin and minerals. 320 children aged 5 months to 36 months will be included in the study. After completion of the study the success rate with diet A, diet B and overall will be calculated and will be compared with that of the control group. The weight gain or loss of the patients of intervention group will also be compared with that of the control group. The factors related to treatment failure will also be analysed. This treatment algorithm might help to establish a rationale and effective treatment of persistent diarrhoea at home.

KEY PERSONNEL (List names of all investigators including PI and their respective specialties)

Name	Professional Discipline/Specialty	Role in the Project
1. [name]	SMO Gr I/Gastroenterology	Principal Investigator
2. [name]	SMO Gr II/Paediatrics	Co-Investigator
3. [name]	Scientist/Epidemiology	Co-Investigator
4. [name]	Interim Director/Paediatrician	Co-investigator

DESCRIPTION OF THE RESEARCH PROJECT

Hypothesis to be tested:

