Describe in detail the methods and procedures that will be used to accomplish the objectives and specific aims of the project. Discuss the alternative methods that are available and justify the use of the method proposed in the study. Justify the scientific validity of the methodological approach (biomedical, social, or environmental) as an investigation tool to achieve the specific aims. Discuss the limitations and difficulties of the proposed procedures and sufficiently justify the use of them. Discuss the ethical issues related to biomedical and social research for employing special procedures, such as invasive procedures in sick children, use of isotopes or any other hazardous materials, or social questionnaires relating to individual privacy. Point out safety procedures to be observed for protection of individuals during any situations or materials that may be injurious to human health. The methodology section should be sufficiently descriptive to allow the reviewers to make valid and unambiguous assessment of the project. **(DO NOT EXCEED TEN PAGES, USE CONTINUATION SHEETS).**

Design: This is a randomized, controlled, home-based intervention study.

Patients selection: Children attending the out-patient department of ICDDR,B hospital will be considered for selection into the study.

Inclusion criteria:

- a) Age 5 months to 36 months
- b) Duration of diarrhoea > 14 days
- c) Dehydration status-some or nil according to WHO criteria
- d) Written informed consent obtained from parents or legal guardian
- e) Accessible distance (within 15 km radius from ICDDR,B)

Exclusion criteria:

- a) Signs of systemic illness or other severe illnesses requiring hospital-based care (sepsis, severe pneumonia, meningitis, severe hyponatraemia or hypokalaemia)
- b) Severe malnutrition - wt/age <60% with or without edema.
- c) Patients with severe dehydration
- d) Bloody diarrhoea

Observation period:

All patients attending the outpatient department of ICDDR,B from 8 a.m. to 2 p.m. with history of persistent diarrhoea will be screened for eligibility for this study following the inclusion and exclusion criteria. The children who are eligible will initially be observed for 4 hours. A detailed clinical history will be recorded, and physical examination including anthropometry will be done. Children with some dehydration will be rehydrated with WHO-ORS.

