At home, care-givers will record on a diarrhoea diary the frequency of stool each 24 hours, the stool consistency and time of cessation of diarrhoea. (Definitions below). After 7 days if diarrhoea continues, caregivers will be trained to prepare Diet B and will be instructed to feed Diet B - a milk free diet containing rice-cereal, vegetable oil, egg albumin and glucose mixture. The second diet (B) will also be fed for 7 days. For partially breastfed children the diets will be offered to attain energy intake >75 kcal/kg/day and for non-breastfed child the energy intake will be 110 kcal/kg/day. In addition multivitamin drops and zinc acetate are standard therapy for PD patients and will be given routinely to all children from the beginning of the study and for the following three weeks (Table 2). The dosage of multivitamin syrup will be 1 ml twice daily and Zinc acetate 10 mg twice daily. Oral rehydration with standard WHO-ORS will continue to maintain hydration to replace ongoing liquid stool losses until cessation of diarrhoea. The number of ORS packets used will be recorded.

On day 7 after beginning of diet A, if the patients are found to have normal stool (soft or formed), they will continue diet A.

After 7 days of second dietary regime, if diarrhoea persists, the patients will be admitted to the inpatient department for further evaluation and management according to the standard hospital practice at ICDDR,B.

Control group

The patients under control group will receive standard management which is advised to take WHO-ORS at home for maintenance of hydration and to continue his/her usual diet or as advised by hospital physician.

Follow-up:

All patients will be followed-up by home visits on every alternate day up to day 15 and then every 2 weeks thereafter up to 4 weeks. The children will be examined thoroughly including anthropometry at every follow up. Study personnel will also monitor the preparation of diet at home. Samples of prepared diet will also be collected and stored in deep freezer for quality study (e.g. composition and calories).

Fig. 1

DIETARY TREATMENT ALGORITHM

[figure not shown]

Table 1. Composition of study diets

Diet A		Diet B	
Milk/Suji/Litre (>4 mo age group)		Full-Strength Rice Suji/L	
Whole milk powder	40 g	Rice powder	60 g
Rice powder	40 g	Egg white	100 g (four)
Sugar	25 g	Oil (Soya)	30 ml
Oil (Soya)	25 g	Glucose	35 g
Mag. Chloride	0.5 g	Kcl	01 g
Potassium chloride	01 g	Mag. Chloride	0.5 g
Calcium	02 g	Calcium	02 g

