After cooked volume	1000 ml	After cooked volume	1000 ml
Energy	67kcal/100ml	Energy	70 kcal/100 ml
Protein	4.4 gm/100ml	Protein	1.88 g/100 ml
PER*	8%	PER	10%

Table 2. Composition of Multivitamin drop (Composition per 1 ml)

Vitamin A U.S.P.	5000 IU
Vitamin D B.P.	640 IU
Ascorbic Acid (C) B.P.	50 mg
Thiamine Hcl (B ₁)	1.6 mg
Riboflavin Sodium Phosphate (B ₂) B.P.	1.37 mg
Pyridoxine B.P. (B ₆) U.S.P.	1.0 mg
Nicotinamide B.P.	10.0 mg
D-Panthenol U.S.P.	5.0 mg
Folic acid	0.25 mg

Justification of selection of diet A in the beginning

Dietary treatment algorithm is a well recognised treatment schedule for the nutritional management of children suffering from persistent diarrhoea. In ICDDR hospital, this treatment algorithm is also being followed. Justification of using Diet A initially is that this diet is easy to prepare, culturally acceptable, less modified as compared to Diet B. and less expensive (1 L Diet A costs Tk. 18.00 vs. Tk. 26.00 for Diet B).

Study withdrawal

Patients will be considered withdrawn from the study if a) their parents withdraw informed consent, or b) needs hospital care.

Patients will be considered for hospital care for the following reasons:

a) appearance of signs of some dehydration b) signs of severe infections (e.g. fever, cough, respiratory distress, tachycardia, tachypnoea, reluctant to feeding etc. c) signs of electrolyte imbalance (e.g. less responsive to environments or irritability, abdominal distensions etc.). After hospitalisation, the patients will be managed according to the standard hospital practice. Patients will be followed up even after withdrawn from the study. Data obtained from the withdrawn patients will also be included in the analysis upto the time of withdrawal.

Sample size

Sample size was calculated on the basis of two major outcome variables:

- a) success rate of diet therapy
- b) Growth faltering (percentage of patients experiencing weight loss during the study periods).

Based on the study (21) the sample size of this study is determined to be of 137 in each group on anticipated success rate (combining success of Diet A and Diet B) of 80% in the intervention group against an arbitrary standard success rate of 65% in the control group, considering a significance level of 5% and power of 80%. Assuming a dropout of 15%, a total sample of 320 patients was calculated.

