We are not expecting significant difference in recovery rate on diet A and the control. However, if the difference is 20% or more, then the present sample size will be enough to detect the significant difference.

Thirty percent of children under control group is anticipated to experience weight loss as opposed to 10% in the intervention group during the study periods. Considering a significance level of 5% and 80% power, the sample size in each group is calculated as 60.

Finally, we consider the total sample size for this study as 320.

Organization of the trial

Patients attending in the treatment centre of ICDDR,B will be evaluated for recruitment for study.

Study Schedule

The study will be started after the approval of RRC and ERC and allocation of budget. The first two months will be utilized for staff recruitment, training and pretrial. 20 months will be needed for patients study. Last 2 months will be utilized for data analysis and reporting of the study results.

Definition

Diarrhoea: Three or more abnormal stools (loose or watery) during a 24-hour period.

Stool consistency: Abnormal stool - loose/watery or abnormal as considered by mother.
Normal stool - soft/formed or normal as considered by mother.

Cessation of diarrhoea: Last abnormal stool followed by normal stool at least for three days.

Success of diet therapy: Cessation of diarrhoea within 7 days of starting of the modified diet (diet A or diet B).

Facilities Available

Describe the availability of physical facilities at the place where the study will be carried out. For clinical and laboratory-based studies, indicate the provision of hospital and other types of patient's care facilities and adequate laboratory support. Point out the laboratory facilities and major equipments that will be required for the study. For field studies, describe the field area including its size, population, and means of communications. (TYPE WITHIN THE PROVIDED SPACE).

ICDDR,B treatment centre will be used for patients recruitment, observation, and training of the caregivers of the patients.

Data Analysis

Describe plans for data analysis. Indicate whether data will be analyzed by the investigators themselves or by other professionals. Specify what statistical softwares packages will be used and if the study is blinded, when the code will be opened. For clinical trials, indicate if interim data analysis will be required to monitor further progress of the study. (TYPE WITHIN THE PROVIDED SPACE).

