Statistical analysis

Statistical analysis will be done using SPSS/PC software. Percentage of success of treatment for each dietary intervention and overall success rate will be calculated. Relative risk ratios and their associated 95% confidence intervals will be calculated to identify variables (e.g. inappropriately making and feeding the diet, associated other infections, education of mothers, family income, no. of children in the family, source of drinking water, antibiotic use before admission, type of dehydration before intervention, frequency of stool etc.) that were related to the treatment failure. Overall success rate (the number of patients recovered at the end of 10 days) in the intervention group will be compared with that of control group. The number of patients lost weight will also be compared between the groups.

Adjusted analysis will be done by constructing life tables of the two groups and will be compared by log rank test.

Ethical Assurance for Protection of Human Rights

Describe in the space provided the justifications for conducting this research in human subjects. If the study needs observations on sick individuals, provide sufficient reasons for using them. Indicate how subject's rights are protected and if there is any benefit or risk to each subject of the study.

This intervention study will be conducted among the children under 5 years of age because these children are the sufferers from this illness of persistent diarrhoea. Written informed consent will be duly signed by the parents or legal guardians.

There is no risk for this intervention on the other hand they might be benefited from this intervention.

Use of Animals

Describe in the space provided the type and species of animal that will be used in the study. Justify with reasons the use of particular animal species in the experiment and the compliance of the animal ethical guidelines for conducting the proposed procedures.

Not applicable.

Literature Cited

Identify all cited references to published literature in the text by number in parentheses. List all cited references sequentially as they appear in the text. For unpublished references, provide complete information in the text and do not include them in the list of Literature Cited. There is no page limit for this section, however exercise judgment in assessing the "standard" length.

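### Weight loss, one of the two outcomes that size the trial, has no fixed assessment day or reference weight and is analysed only as a yes/no count, although weights are taken at every visit

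*Protocol*

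**What the plan says.** The Sample size section lists two major outcomes. The second is "Growth faltering (percentage of patients experiencing weight loss during the study periods". Its planning assumption is "Thirty percent of children under control group is anticipated to experience weight loss as opposed to 10% in the intervention group during the study periods", followed by "Considering a significance level of 5% and 80% power, the sample size in each group is calculated as 60".

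The Statistical analysis section plans "The number of patients lost weight will also be compared between the groups". The Project Summary is broader: "The weight gain or loss of the patients of intervention group will also be compared with that of the control group". It gives no scale, visit or method.

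Weights are plentiful. Under Follow-up, home visits run on alternate days to day 15 and then fortnightly to 4 weeks, and "The children will be examined thoroughly including anthropometry at every follow up".

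At entry, children with some dehydration are eligible. The Observation period section describes a 4-hour stay in which "physical examination including anthropometry will be done. Children with some dehydration will be rehydrated with WHO-ORS". No later baseline weight is mentioned.

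The Study withdrawal section uses a withdrawn child's data only until the point of withdrawal, yet says that such children continue to be followed.

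**The concern.** Three things are left loose in an outcome that the Protocol otherwise fixes, with expected rates and a sample size.

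- **Period.** Loss at any visit, loss at day 15 and loss at week 4 are different outcomes with different expected percentages. The planned 30% and 10% cannot be tied to any one of them.
- **Reference weight.** With a cut exactly at zero, a child's classification depends on the starting weight. If that weight precedes rehydration, replaced fluid later counts as weight gain.
- **Scale.** A series of measured weights is reduced to one yes/no per child.

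At stake is whether the second major outcome has a single pre-specified answer, and whether it could show a benefit smaller than the large one assumed.

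**Working it through.** **1. The Protocol's own figure.** Inputs from Sample size: 30% and 10%, significance level 5% (taken as two-sided), power 80%.

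- Pooled formula: n = [1.960·√(2·0.20·0.80) + 0.842·√(0.30·0.70 + 0.10·0.90)]² / 0.20² = 61.6, so 62 per arm.
- Unpooled formula: n = (1.960 + 0.842)²·(0.21 + 0.09) / 0.20² = 58.9, so 59 per arm.

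The stated 60 lies between these and is reproduced.

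**2. Power at the size actually planned.** The total is 320, or 160 per arm. With 15% dropout, 160 × 0.85 = 136. Power for 30% against 10% is Φ{[0.20 − 1.960·√(2·0.20·0.80/136)] / √(0.30/136)} = Φ(2.23) = 98.7%.

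**3. The same effect on the continuous scale.** Assumption (not in the Protocol): weight change is normal with equal SD in both arms. If 30% and 10% lie below zero, the means differ by z(0.90) − z(0.70) = 1.282 − 0.524 = 0.757 SD. Comparing means then needs n = 2·(1.960 + 0.842)² / 0.757² = 27.4, so 28 per arm. The ratio is 28/62 = 0.45, so the yes/no cut discards about 55% of the information (53% against the unpooled 59). Baseline adjustment and repeated weights are not counted here.

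**4. A smaller effect.** The Protocol gives no alternative effect, so the shift is an assumption, shown over a range. Control is held at 30%, with 136 per arm. The intervention proportion is Φ(−0.524 − shift). Yes/no power uses the formula in step 2. Power for means is Φ(shift·√(136/2) − 1.960).

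| Assumed shift (SD) | Proportions losing weight | Power, yes/no | Power, mean change |
|---|---|---|---|
| 0.25 | 30% vs 21.9% | 33% | 54% |
| 0.35 | 30% vs 19.1% | 55% | 82% |
| 0.50 | 30% vs 15.3% | 83% | 98% |
| 0.757 (Protocol's rates) | 30% vs 10% | 99% | above 99.9% |

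**5. Possible end points in the text.**

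- Day 10: the time at which overall success is counted (Statistical analysis).
- Day 15: the last alternate-day visit (Follow-up).
- Week 4: the end of home visits (Follow-up).
- Four weeks after diarrhoea resolves, which differs by child (Answer to Reviewer # I, item 4).

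Nothing in the Protocol ties the weight outcome to one of these. Because data stop at withdrawal, a withdrawn child also has a shorter window in which a loss can be recorded.

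**6. Reference weight.** Measurement and rehydration stand in consecutive sentences with no stated order. If the weight comes first, regained fluid hides some losses. By randomisation this should happen about equally in both arms, so the expected effect is a smaller difference, not one tilted towards either arm. Its size would need the share of children with some dehydration and the weight they regain. The Protocol gives neither, so no figure is offered.

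**The case against.** The case on the other side is substantial.

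- **Power is ample as planned.** At 30% against 10% the count has about 99% power. The success outcome, at 137 per arm, drives the sample size, so a more efficient weight analysis saves no patients. This stands. The gain is protection against a smaller true effect, and the 0.35 SD example is an illustration.
- **Any weight loss is an interpretable event, and details may sit in a SAP.** The sponsor calls the outcome growth faltering, the Project Summary leaves room for a continuous comparison, and model and covariates are commonly left to the SAP. This stands in part. However, the Statistical analysis section commits to the count, and the outcome's rates and sample size are fixed here around a period that is not.
- **Pre-rehydration weighing is not established.** A reader might infer from the sentence order that children are weighed first and that real losses are therefore hidden. The text states no order. What it supports is that the reference weight is unspecified.
- **Hospital care need not contaminate the late weights.** A reader might infer that week-4 weights in the intervention arm reflect inpatient management, because children still ill after Diet B are admitted. Needing hospital care is a ground for withdrawal and data stop there, so on that reading weights after admission would not enter the analysis. The remaining difficulty is the cut-off itself: it shortens observation for withdrawn children even though they are still followed.

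**Conclusion.** The point holds as one of definition and efficiency. One of the two sizing outcomes has no fixed day and no fixed reference weight, is exposed to unequal observation time through the withdrawal rule, and is planned only as a count from repeated measured weights.

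The loss of information is about 55% if weight change is roughly normal with equal SD; a skewed distribution would change that figure. The outcome is not underpowered on the Protocol's own rates. Power becomes a problem only for smaller effects, such as 55% against 82% at an assumed 0.35 SD. Dilution from rehydration is possible, would be expected in both arms, and cannot be sized from the document. The change is worth making because it costs very little.

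**What to change.** - **Baseline:** use a weight taken at the end of the 4-hour observation, after any rehydration, for every child.
- **Main weight comparison:** change from that baseline to day 15, adjusted for baseline weight and age stratum (ANCOVA, or a repeated-measures model using the alternate-day weights).
- **Population:** all randomised children. Include weights collected after withdrawal, since follow-up continues, and amend the rule that ends data use at withdrawal for this outcome. Two 7-day diets end at about day 14, so a day-15 weight is little affected by admission after Diet B.
- **Supporting summary:** the proportion below baseline at day 15, by arm.
- **Wording:** make the Project Summary, Sample size and Statistical analysis sections describe this same outcome.

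Cost: one extra weighing while the child is still in the clinic, and slightly more analysis work. Sample size and visit schedule do not change.

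### The failure-factor analysis rests, on its natural reading, on crude risk ratios for nine or more factors, so it can flag social markers with no effect of their own; it also mixes diet-making errors with baseline factors

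*Protocol*

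**What the plan says.** The Project Summary announces the analysis as an addition to the comparison of the groups: "The factors related to treatment failure will also be analysed".

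The Statistical analysis section names the tool: "Relative risk ratios and their associated 95% confidence intervals will be calculated to identify variables" "that were related to the treatment failure". Six factors come first: "inappropriately making and feeding the diet, associated other infections, education of mothers, family income, no. of children in the family, source of drinking water". Three more follow and the list stays open: "antibiotic use before admission, type of dehydration before intervention, frequency of stool etc". That makes at least nine.

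The section does not say which arm or arms are analysed. It names no multivariable or stratified model for the factors and no comparison of a factor's effect between arms.

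The word adjusted appears once in that section: "Adjusted analysis will be done by constructing life tables of the two groups and will be compared by log rank test". The appended replies (item 5) repeat this. It is a comparison of the two arms and involves none of the listed factors.

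**The concern.** A crude risk ratio for one factor carries part of the effect of any other factor correlated with it. Mother's education, family income, number of children and source of drinking water plausibly reflect the same household circumstances. If only one of them matters, the others can still show a ratio above 1 with an interval that excludes 1.

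The list also mixes two kinds of variable. Wrong making and feeding of the diet can be observed only after randomisation, and only in the intervention group, because only those mothers receive the ingredients (Case management). It cannot be a baseline predictor and has no counterpart in the control arm. Antibiotic use before admission and dehydration before intervention are true baseline factors.

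At stake is the credibility of an announced secondary result. A marker with no effect of its own could be reported as related to failure of home treatment.

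**Working it through.** **Inputs from the Protocol (Sample size).** The design assumes an "anticipated success rate (combining success of Diet A and Diet B) of 80% in the intervention group" and 65% in control, 137 per group, 15% dropout and 320 in total. Failure is taken here as the complement of success.

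**The plan's own figure.** Two-sided 5%, 80% power, unpooled: (1.960 + 0.842)² × (0.80×0.20 + 0.65×0.35) / 0.15² = 135.2, so 136 per group. The pooled formula gives 138. The stated 137 lies between them. For dropout, 274/0.85 gives 323 and 274×1.15 gives 316; the stated 320 lies between. The inputs can be used as they stand.

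**Expected failures.** Evaluable per arm: 160 × 0.85 = 136.
- Intervention: 0.20 × 136 = 27.
- Control: 0.35 × 136 = 48.
- Together: 75.

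**Multiplicity alone.** The "associated 95% confidence intervals" imply a 5% two-sided level per factor. If no factor matters and the nine tests are independent, the chance of at least one flag is 1 − 0.95⁹ = 37%. Correlation lowers this: simulated values are 22-35% for latent correlation 0.3 to 0.7.

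**Confounding alone.** Assume two binary factors, each split 50/50, with latent correlation ρ. One has true risk ratio R = 2; the other is inert. The probability that both are present is q = 1/4 + arcsin(ρ)/(2π). Put s = q/0.5. The expected crude ratio of the inert factor is (sR + 1 − s) / ((1 − s)R + s).
- ρ = 0.5: q = 0.333, s = 0.667, ratio = 1.667/1.333 = 1.25.
- ρ = 0.7: q = 0.373, s = 0.747, ratio = 1.747/1.253 = 1.39.

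Simulated, that one inert factor is flagged in 9-17% of trials in the intervention arm (137 to 160 children) and 23-44% over both arms (320 children). Adjusting for the true factor (Mantel-Haenszel) brings this to 4-5%.

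**Several social factors together.** Simulation with 136 per arm, failure 20% and 35%, and eight binary factors. Four are correlated; one of these has risk ratio 2 and three are inert. In each cell the first figure is for ρ = 0.5 and the second for ρ = 0.7.

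| Analysis | True factor found | At least one of three inert factors flagged |
|---|---|---|
| Crude, intervention arm | 46% / 46% | 22% / 29% |
| Crude, both arms | 92% / 91% | 41% / 61% |
| Multivariable, both arms | 87% / 76% | 14% / 15% |

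In the multivariable model each inert factor is flagged about 5-7% of the time. Repeat runs moved these figures by up to about three percentage points. A multivariable model in the intervention arm alone finds the true factor only 40% / 36% of the time.

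**Support for a model.** With nine factors plus arm, 75/10 = 7.5 failures per term. In the intervention arm alone, 27/9 = 3 per factor.

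**Power of an arm-by-factor term.** Assume risk ratio 2 on the diet and 1 in control, with 68 children per cell. The four cell risks are 0.267, 0.133, 0.35 and 0.35. The variance of the log ratio of ratios is 0.040 + 0.096 + 0.027 + 0.027 = 0.191, so the standard error is 0.437. Then ln 2/0.437 = 1.59, and power is Φ(1.59 − 1.96), about 35%.

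**The case against.** The strongest reply is that the fault is inferred. The Protocol does not say that the ratios are unadjusted or taken singly; a risk ratio can be adjusted, and covariate models and cut-points are often left to a SAP, which is not at hand. The analysis is also secondary: it is not one of the two sample-size outcomes, and the text speaks only of variables related to failure. Part of this stands and sets the severity. It does not remove the point, because the Protocol itself chose the tool and used the word adjusted for a different analysis.

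A reader might also infer stronger things that the documents do not support:

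- *That the plan will flag inert factors, or cannot tell poor prognosis from failure of the diet.* It can flag them, at rates that depend on assumed correlations. A control arm exists and the factor analysis is not restricted to one arm, so baseline factors could be examined in both. The plan simply does not provide for it.
- *That lack of adjustment makes a true factor more likely to be missed.* It does not. Low detection in the intervention arm comes from about 27 failures, and adjustment there lowers it further. Over both arms, crude ratios find the true factor slightly more often than the model does.
- *That 37% is the false-flag rate.* It is the figure for nine independent null tests, and correlation reduces it.
- *That infections in the list arise after randomisation.* No time is given. The initial assessment includes physical examination, stool tests and urine analysis, so they may be baseline findings.
- *That the plan claims to explain why home treatment fails.* It claims association only.

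**Conclusion.** The point holds as a minor one. On the natural reading, crude ratios are the sole means of identifying failure factors. Where factors are correlated, these ratios can single out some that have no effect of their own. Like for like over both arms, the chance of flagging at least one of three inert social factors is about 41-61% crude and 14-15% in a multivariable model. If the crude analysis is confined to the intervention arm, it is 22-29%. These figures rest on an assumed risk ratio of 2, latent correlation of 0.5 to 0.7 and 50/50 factor splits; the Protocol gives none of them. That diet-making errors arise after randomisation and only in the intervention arm needs no such assumption. The randomised comparisons of success and weight loss are not affected.

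**What to change.** - Keep the crude ratios. Beside them, report adjusted risk ratios from one model (modified Poisson with robust standard errors) over both arms, with treatment arm and a short prespecified list of baseline factors.
- Keep income, number of children and baseline stool frequency continuous. State that stool frequency is the baseline value, since the list gives no time point.
- Report errors in making and feeding the diet, and any infections that arise during the study, separately and as descriptive.
- Label the whole analysis exploratory, including any arm-by-factor term, whose power is about 35% even for a sizeable difference.

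The cost is a few sentences and a little more analysis work, with no new data. The downside is somewhat wider intervals, a few points of lost detection against pooled crude ratios, and only about 75 expected failures to support the model. That is why the list of factors should be short.

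### The overall-success comparison stops at day 10, but the algorithm and the 80% rate behind the sample size need 14 days

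*Protocol*

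**What the plan says.** All places are in the Protocol.

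- **Statistical analysis:** "Overall success rate (the number of patients recovered at the end of 10 days) in the intervention group will be compared with that of control". This section also plans life tables compared by a log-rank test, with no day-10 limit, and a comparison of the numbers who lost weight.
- **Case management, intervention group:** Diet A is fed for 7 days. If diarrhoea continues, the child moves to Diet B, and "The second diet (B) will also be fed for 7 days". The algorithm therefore ends at day 14.
- **Definition, success of diet therapy:** "Cessation of diarrhoea within 7 days of starting of the modified diet (diet A or diet B"). A Diet B success can occur up to day 14.
- **Definition, cessation of diarrhoea:** "Last abnormal stool followed by normal stool at least for three days".
- **Sample size:** 137 per group, from an "anticipated success rate (combining success of Diet A and Diet B) of 80% in the intervention group". For controls the assumed figure is set "against an arbitrary standard success rate of 65% in the control group", at 5% significance and 80% power. The total is 320 after a 15% allowance for dropout. On Diet A alone the section says: "We are not expecting significant difference in recovery rate on diet A and the control". It adds that a difference of 20% or more could be detected.
- **Follow-up:** home visits on alternate days to day 15 in all patients, then two-weekly up to 4 weeks.

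**The concern.** The protocol itself fixes the time point of the main efficacy comparison, so this is not a detail left for a later analysis plan. The point chosen conflicts with the feeding schedule, the definition of success and the basis of the sample size, and nothing elsewhere in the document resolves the conflict.

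At day 10 a child on Diet B is not yet halfway through it. If Diet A is not expected to differ significantly from control, much of the 15-point advantage has to come from Diet B, and that is the part a day-10 count cuts short. The comparison could then miss a benefit of the full algorithm that the trial was sized to find.

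The definition of success does not settle the matter for the control arm. Its clock starts with a modified diet, which controls never receive.

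**Working it through.** **1. The plan's own figure.** Inputs from Sample size: p1 = 0.80, p2 = 0.65, alpha 5% (taken as two-sided; the protocol does not state sidedness), power 80%. With the mean rate p̄ = 0.725:

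n = [1.96 × √(2p̄(1−p̄)) + 0.842 × √(p1(1−p1) + p2(1−p2))]² / (p1−p2)²

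= [1.96 × 0.6315 + 0.842 × 0.6225]² / 0.15² = 137.9, or 138 per group.

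The stated 137 reproduces to within one patient, and power at 137 is 79.7%. For dropout, 274/0.85 = 322 and 274 × 1.15 = 315, so 320 is reasonable. The arithmetic is sound. The question is whether these rates apply at day 10.

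**2. How much of Diet B a day-10 count can see.** Diet A occupies days 1-7 and Diet B days 8-14.

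- If the three normal days must be complete by day 10, they are days 8, 9 and 10 at the latest. The last abnormal stool is then on day 7 or earlier, and no Diet B success counts.
- If cessation is dated to the last abnormal stool and confirmed later, Diet B can contribute on days 8-10, which is 3/7 of its window.

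The definition does not say which dating applies.

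**3. Power at day 10.** The protocol gives no day-10 rate for either arm and no time point for the 65%, so every row below is an assumption. Power at 137 per arm, two-sided 5%, is

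Φ{[|p1−p2|√n − 1.96√(2p̄(1−p̄))] / √(p1(1−p1) + p2(1−p2))}

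| Assumption | Day-10 rates | Power |
|---|---|---|
| Diet A equals control; no Diet B success counted | 65% vs 65% | about 5% (the type I error, half in each direction) |
| Diet A reaches 70%; control 65%; no Diet B success counted | 70% vs 65% | 14% |
| Diet A equals control at 65%; 3/7 of Diet B's 15 points counted (65 + 15 × 3/7) | 71.4% vs 65% | 21% |
| Control at constant hazard to 65% at day 14; Diet A equal to control to day 7; Diet B then at constant hazard to 80% at day 14 | 62.8% vs 52.8% | 39% |
| Diet A reaches 75%; control 65%; no Diet B success counted | 75% vs 65% | 44% |
| 15-point gap already present, both rates lower | 75 vs 60, 70 vs 55, 65 vs 50 | 76%, 73%, 71% |
| Constant hazard in each arm to 80% and 65% at day 14 | 68.3% vs 52.8% | 75% |

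For the fourth row, control recovery by day 10 is 1 − 0.35^(10/14) = 52.8%. The proportion unrecovered at day 7 is 0.35^(1/2) = 0.592 in both arms. Intervention recovery by day 10 is 1 − 0.592 × (0.20/0.592)^(3/7) = 62.8%.

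The last two rows need most of the benefit to arrive before Diet B has run its course. That sits uneasily with the protocol's expectation for Diet A.

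**4. At day 14.** If 80% and 65% are read as day-14 rates, the stated inputs apply unchanged, with 79.7% power at 137 per arm.

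**The case against.** A reader might infer that Diet B cannot contribute to the day-10 count at all. The documents do not establish that. It holds only if the three normal days must be finished by day 10. Caregivers record the time of cessation and visits go on past day 10, so cessation could be dated to the last abnormal stool and confirmed afterwards. Diet B then contributes for days 8-10.

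A reader might also infer that the expected day-10 difference is zero and a null result is to be expected. That goes too far for three reasons.

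- Not expecting a significant difference is not the same as expecting equality. The sentence that follows it is about what size of difference could be detected, and a Diet A rate of 70% or 75% against 65% would fit it too.
- The 65% has no time point. If both rates are lower at day 10 and the gap persists, power falls only to 71-76%.
- Other analyses are not limited to day 10. The log-rank comparison can capture later Diet B recoveries. The weight-loss outcome (30% vs 10%) is one of the two outcomes used for sample size, and its power at 137 per arm is about 99%.

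These points limit the size of the problem but leave the contradiction in place. The log-rank test is described only as an adjusted analysis, and the sample size is built on proportions. No scenario tried above keeps the stated 80%.

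**Conclusion.** The contradiction stands and needs no assumption: a 10-day count cannot represent a strategy of 7 plus 7 days, a success definition that reaches day 14 for Diet B, or a sample size built on both diets combined.

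Its cost in power does rest on assumptions. Against 79.7% for the design as stated, day-10 power at 137 per arm ranges from about 5% to about 76%. It falls at the low end if Diet A does little better than control, and at the high end if a gap of about 15 points is already present by day 10. No single figure in that range can be called the trial's power, because the protocol supplies no day-10 rates. The fault affects the main comparison of efficacy and should be corrected before the analysis is fixed.

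**What to change.** In the statistical analysis section, replace the 10-day count with one definition of overall success used in both arms and counted from randomisation: last abnormal stool within 14 days, followed by at least three days of normal stool. State that the 80% and 65% in the sample size refer to this definition.

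Keep the stool diary in both arms until about day 17, so that cessation on day 14 can be confirmed (days 15, 16 and 17 normal). The protocol gives no end date for the diary. Alternate-day visits already run to day 15.

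Day 7 may be kept as a secondary randomised comparison of Diet A with control.

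The timing of Diet B must also be reconciled within the document. Case management starts training for it after 7 days, whereas item 3 of the Answer to Reviewer section has mothers taught on day 6 after 5 days without improvement. The outcome window should then cover both diet periods as finally scheduled.

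Cost: wording in the definition, sample size and analysis sections, and a few more diary days. No extra patients are needed.
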